Risk of incidental findings: Tests performed by certified clinical laboratories may provide results that indicate a clinically significant or medically actionable condition might be present. In these circumstances, the Principal Investigator or other designated licensed medical professional at each site will determine if further testing is necessary and will contact participants as detailed in Section 13.4.3.1.

Risk of genetic testing: There is a risk of discovering potentially pathogenic genetic variants of uncertain clinical significance during the study. Results are defined as clinically actionable according to the standards and guidelines defined by the American College of Medical Genetics and Genomics and the Association for Molecular Pathology (ACMB-AMP guidelines). Some whole genome sequencing studies may be performed

in a CLIA-approved lab. The consent form will inform the participant of the potential for actionable results and will ask participants whether they would like to be informed about the presence of actionable potentially pathogenic genetic variants. For participants who elect to be informed of these genetic results, the genetic variant discovered will be shared with the site PI or designated study personnel, who will use their local process and policies for re-identification of the participant and referral if needed for evaluation, which may include involvement of their local genetics team and/or the participant's cardiologist or other caregivers.

There is some chance that analysis of the relationship of genetic findings to outcomes could cause psychological distress. Some people involved in genetic studies feel anxious about the possibility of carrying (or their child carrying) an altered gene that may place them at risk or that might be passed on to subsequent generations.

4.2 Known Potential Benefits

There are no known potential benefits to this study to subjects, but there is a potential benefit to public health. Healthcare physicians may have a better understanding of how to meet the needs of COVID-19 survivors more effectively.

5 Objectives and Purpose

The purpose of this study is to characterize the spectrum of PASC symptoms and define the incidence, prevalence, and underlying mechanism of PASC in the adult across multiple sites in the United States. The specific aims are to:

- Characterize the incidence and prevalence of PASC, including clinical and biological features, severity, and distinct sub-phenotypes, following COVID-19 infection.
- Characterize the clinical course and recovery of sequelae over time and determine associated risk factors for PASC among COVID-19 infected individuals and compared them to uninfected individuals.
- Define the pathophysiology of and mechanisms of post-acute sequelae, including direct and indirect causal effects of COVID-19 infection, and potential modifiers (e.g., sex, age, and race/ethnicity).

We hypothesize that this study will elucidate risk factors(s) that contribute to PASC progression.

6 Study Design

6.1 Study Design

[figure not shown]
This is an ambi-directional longitudinal meta-cohort study (combined retrospective and prospective) to determine the clinical spectrum, progression, prevalence, and incidence of PASC (COVID-19). Individuals with and without COVID-19 infection will be enrolled at varying stages during and after first infection (Figure 1).

We will include subjects who meet our inclusion and none of the exclusion criteria and analyze the core set of questions on demographics, comorbidity, COVID-19 vaccination status, acute COVID-19 clinical course, current clinical condition/symptom, and outcomes as tiered testing. Participants who consent and contribute data to the study will count towards target enrollment numbers.

Figure 1: Enrollment plan for people with infection

Adult recruitment cohorts

[figure not shown]

Many of the participating health centers utilize electronic health record (EHR) systems. This facilitates the pooling of data to ask and answer numerous research questions applicable to the care of subjects with or at risk for COVID-19. Data will be entered into the secure HIPAA compliant REDCap database for analysis and storage.

A subset of participants will be asked to undergo Tier 2 (**Appendix 3**: Tier 2 questions, tests and procedures) and in some cases Tier 3 testing (**Appendix 4**: Tier 3 tests and procedures), if available at the local study site. In order to meet the sample size targets described in Section 12.2 below, participants are organized into four "buckets" based on their COVID-19 infection status and whether or not they present with relevant PASC symptoms. To ensure statistical power to differentiate between each protocol-specified bucket for analysis, this protocol specifically assigns Tier 2 and Tier 3 assessments to participants in each bucket. These assessments are assigned to the appropriate number of infected participants (Bucket 1) and uninfected participants (Bucket 2) who have these relevant symptoms. Then, they are assigned to participants without symptoms by randomly selecting the appropriate number of infected (Bucket 3) and uninfected (Bucket 4) participants. This process is shown in **Table 2**.

Table 2: Distribution of Participants by COVID-19 Infection History and Relevant Symptoms

	Infected subject	Uninfected subject
With relevant symptom(s)	[Bucket 1]	[Bucket 2]
Without relevant symptom(s)	[Bucket 3]	[Bucket 4]

[figure not shown]
All relevant symptoms are described in the corresponding procedure's SOP. As the symptoms that are most relevant to PASC are better understood, RECOVER's subject matter experts refine the list of relevant symptoms for each test. Once the target sample size (see Section 12.2) has been reached with adequate data quality within each bucket, we cease assigning the test to people in that bucket. This ensures that our total enrollment and procedure sample sizes are as small as can be in order to ensure usable data. In other words, this approach allows us to minimize the number of people that we ask to undergo each test and the risk of the study, while maintaining adequate statistical power.

We anticipate that approximately 30% of participants will undergo each Tier 2 test and a maximum of 20% of participants will undergo each Tier 3 test. For Tier 2 testing, a random sample of 5.6% of SARS-CoV-2 infected and 11.4% of uninfected participants will be asked to undergo each Tier 2 test. These percentages may be modified to ensure the correct distribution of PASC and control participants as testing accrues. In addition, some or all participants who meet test-specific clinical criteria set by subject matter experts will be offered the test so that we ensure an adequate number of participants likely to have a positive test for statistical analysis (see Appendix 5: Tier 2 and 3 eligibility, exclusion criteria for additional description of this process). Among the eligible participants, REDCap will assign some or all of those that meet clinical oversample eligibility criteria to the test (at adaptive proportions designed to keep the total number of participants assigned to the test at not more than 30%) and will randomly assign the test to some of the remainder as described above. As RECOVER follows an adaptive study design, the relevant symptoms for each test will be reviewed and updated periodically to ensure the proper proportion and populations are being selected. When relevant symptoms are changed for tests that also allow random assignment, they only affect the proportion of participants with various conditions assigned the test, but do not change the fact that any participant is still eligible and therefore do not change the risk of the study as a whole. Any participant may decline any Tier 2 or Tier 3 test if offered.

It is necessary to have uninfected participants undergoing the Tier 2 and Tier 3 tests so that we can conduct analyses to identify any significant worsening in outcomes among participants with PASC or SARS-CoV-2 infection versus control. It is necessary to have asymptomatic infected participants undergoing the Tier 2 and Tier 3 tests so that we can identify subclinical pathophysiologic changes. However, for the small subset of highest risk Tier 3 procedures, if there are well-established norms in control populations that can be used for comparison, the test will not be offered to uninfected controls and/or to asymptomatic previously infected participants (see **Appendix 5**: Tier 2 and 3 eligibility, exclusion criteria for details of which tests are only offered to symptomatic infected participants).

The REDCap database uses data entered by the sites to assign Tier 2 and Tier 3 assignments to participants at each study visit. REDCap excludes participants with recent SARS-CoV-2 infections, who have already completed the test within the eligible window, or who meet test-specific safety exclusion criteria from selection. After participants initially complete a Tier 2 test, they will be re-assigned this test approximately annually as a follow-up assessment. Minimal risk Tier 3 tests may also be re-assigned approximately annually. More than minimal risk Tier 3 tests will not be offered more than once, except in the case of participants who were enrolled as uninfected and become infected during the course of the study. After infection, these participants may be offered the opportunity to repeat any more than minimal risk Tier 3 tests done while uninfected, as pre- and post-infection data is highly valuable in identifying changes related to SARS-CoV-2 infection. The REDCap database has strict limitations in place so that participants are not assigned a test for which they are eligible if they have completed the same test within the previous four visit windows (approximately annually). This functionality is only effective if REDCap is updated in a timely fashion. Therefore, sites must update REDCap to indicate performance of a Tier 2 or 3 test within six weeks of test conduct.

Site staff are ultimately responsible for ensuring participants do not meet safety exclusion criteria after they have been selected for a test, as not all exclusion criteria are available in REDCap. Pre-test assessments that are conducted once participant is assigned to a test to determine safety exclusion criteria must then be documented in REDCap. SOPs for these tests make clear that ineligible participants might be assigned tests because not all exclusion information is known to REDCap. These safety exclusion criteria are also

available as checklists for site staff in the respective SOP. For all Tier 3 tests that are more than minimal risk, a licensed physician will review the exclusion criteria for that test and confirm that the subject does not meet any of the specified safety exclusion criteria.

Procedures in Tier 3 will only be performed concurrently when clinically appropriate. Complete information regarding how tests will be assigned will be in each assessment's SOP. Tier 2 and 3 procedure eligibility, exclusion criteria, and clinical variance affecting the risk/benefit assessment are found in **Appendix 5**: Tier 2 and 3 eligibility, exclusion criteria.

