Objectives	 Characterize the incidence and prevalence of sequelae of SARS-CoV-2 infection. Characterize the spectrum of clinical symptoms, subclinical organ dysfunction, natural history, and distinct phenotypes identified as sequelae of SARS-CoV-2 infection. Define the biological mechanisms underlying pathogenesis of the sequelae of SARS-CoV-2 infection. 	
Methodology	Ambi-directional longitudinal meta-cohort study (combined retrospective and prospective) with nested case-control studies.	
Endpoint	Primary Endpoints: Presence of candidate PASC symptoms over time (incidence and prevalence). Secondary Endpoints: Biological and recovery trajectories from SARS-CoV-2 infection; organ injury; incident clinical disease.	
Study Duration	Four years	
Subject Duration	Up to four years	

Title	NIH RECOVER: A Multi-site Observational Study of Post-Acute Sequelae of SARS-CoV-2 Infection in Adults	
Population	Infected: Individuals at least 18 years of age meet WHO criteria for suspected, probable or confirmed SARS-CoV-2 infection on or after January 1, 2020.	
	Uninfected: Individuals at least 18 years of age who have never met any of the WHO criteria for suspected, probable or confirmed SARS-CoV-2 infection.	
Number of subjects	12,200 total subjects with SARS-CoV-2 infection and 2,680 total subjects without SARS-CoV-2 infection.	
Statistical Analysis	A flexible study design is proposed to allow modifications to PASC case definition, tiered phenotyping assessments, comparator groups, and/or statistical plan after its initiation to optimize public health impact without undermining validity and integrity of study findings. Modifications in study design may be based on analyses of structured cohort data, unstructured cohort EHR data, and other cohort EHR data.	

2 Key Roles

Principal Investigators Clinical Science Core [name] MS
Helen L. and Martin S. Kimmel Professor of
Advanced Cardiac Therapeutics
Director Heart Failure Programs
NYU Grossman School of Medicine
Leon H. Charney Division of Cardiology
[name]
New York, NY 10016
[contact]

[name]
Professor and Director, Division of Biostatistics
Department of Population Health
NYU Grossman School of Medicine
[name]
New York, NY 10016
[contact]

[name], MHS
Professor, Department of Population Health at
NYU Grossman School of Medicine
Professor, Department of Medicine at NYU
Grossman School of Medicine
Director, Center for Healthcare Innovation and
Delivery Science

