12.2 Sample Size Determination

The following factors were considered in determining the sample size

- Expected frequency of PASC in the SARS-CoV-2 infected population. Population estimates from studies with selection bias currently range from 25-70%; we used 25% as a conservative estimate.
- The desire for the cohort distribution to include a diverse population, with overrepresentation from non-Hispanic Black, Hispanic and Asian populations relative to general population prevalence to account for a higher rate of SARS-CoV-2 infection and PASC in these populations
- The desire to be able to perform subgroup analyses based on characteristics such as age, sex, race/ethnicity, pregnancy, vaccination status and combinations thereof.

Table 7 shows minimal detectable effect sizes for the key study questions both for the full study sample (Tier 1 N=14,880; Tier 2 N=4,464 and Tier 3 N=2,976) and for subgroups of 25% thereof. These sample sizes for Tier 2 and Tier 3 assume that 25% of infected subjects will have abnormal symptoms. It is further assumed that all infected subjects with abnormal symptoms will progress to Tier 2 (N=3,050) and 5.6% of infected subjects without symptoms will progress to Tier 2 (N=512). Among uninfected subjects, 26.8% (N=718) will progress to Tier 2. 68% of infected subjects with abnormal symptoms will progress to Tier 3, and 3.8% of infected subjects without symptoms will progress to Tier 3. Among uninfected subjects, 18.2% will progress to Tier 3. The infected cohort is expected to include 1,867 pregnant individuals and the uninfected cohort is expected to include 583 pregnant individuals.

Table 7: Sample size calculations

					Min detectable ES*	
Tier	Comparison groups		Effect of interest	Assumptions	Full sample	25% subgroup (e.g. inpatients, Hispanic individuals, etc.)
1	Infected	Uninfected	Difference in risk of PASC between infected and uninfected	Risk of PASC in infected: 25%	3.50%	6.80%
1	Infected w/ RF	Infected w/out RF	Risk difference for PASC in infected with RF vs. without RF	Prevalence of RF: 20%, risk of PASC in infected, RF+: 30%	3.90%	7.60%
1	Pregnant infected	Non- pregnant infected	Risk difference for PASC in pregnant infected versus non- pregnant infected	Risk of PASC in non-pregnant infected: 25%	4.10%	8.00%
1	PASC+ w/ RF	PASC+ w/out RF	Difference in proportion who recover from PASC for those with and without a risk factor	Prevalence of RF: 20%, probability of recovery in PASC+ w/out RF: 0.50	8.70%	17.20%

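### The 30% Tier 2 limit counts tests assigned, but the Tier 2 N of 4,464 needs 30% tested; the PASC+ precision and recovery rows of Table 7 likewise allow for almost no attrition

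*Protocol*

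**What the plan says.** **Assignment and testing.** Section 6.1 states the expectation "We anticipate that approximately 30% of participants will undergo each Tier 2 test". Later in the same paragraph it describes adaptive proportions "designed to keep the total number of participants assigned to the test at not more than 30" per cent. The first counts people tested; the second counts people assigned.

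**Stopping rule.** The preceding paragraph of section 6.1 ends assignment bucket by bucket, once the section 12.2 target has been met with data of adequate quality. That rule counts usable tests.

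**Sources of shortfall.** Section 6.1 also says "Any participant may decline any Tier 2 or Tier 3 test if offered", and that "ineligible participants might be assigned tests because not all exclusion information is known to REDCap". No completion rate is given.

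**Sample size.** Section 12.2 gives "Tier 1 N=14,880; Tier 2 N=4,464 and Tier 3 N=2,976". Its Tier 2 group counts are 3,050 infected with symptoms (all of them), 512 infected without symptoms and 718 uninfected.

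**Recovery.** The fourth row of Table 7 concerns "Difference in proportion who recover from PASC for those with and without a risk factor", with detectable differences of 8.7% in the full sample and 17.2% in a 25% subgroup. Section 6.1 says "Participants who consent and contribute data to the study will count towards target enrollment numbers", and section 7.4 defines loss to follow-up. Section 12.2 makes no allowance for loss.

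**The concern.** If 30% is the ceiling on assignments and also the number to be tested, any refusal or late exclusion leaves the tested number short of the stated N. Section 6.1 does not say whether the ceiling or the bucket target governs when the two conflict. Table 7 would then describe a best case, with no stated rate from which to judge the likely one.

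The recovery row has the same weakness from another cause. Recovery is observed only in follow-up, but enrolment is counted on contributing any data.

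**Working it through.** **Inputs.** The Protocol Summary gives "12,200 total subjects with SARS-CoV-2 infection and 2,680 total subjects without SARS-CoV-2 infection", together 14,880. Section 12.2 assumes 25% PASC in the infected: 0.25 × 12,200 = 3,050. Table 7 assumes a feature rate of 50%, risk-factor prevalence of 20% and recovery probability of 0.50.

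**Inferred inputs.** The protocol states neither alpha nor power. Of the combinations tried (alpha 0.05 or 0.01, power 80% or 90%), only two-sided 0.01 with 90% power fits the rows reproduced below.

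**Formulas.** The detectable difference d solves

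d = 2.576 × √[p̄(1−p̄)(1/n₁+1/n₂)] + 1.282 × √[p₁(1−p₁)/n₁ + p₂(1−p₂)/n₂],

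where p₁ = 0.5, p₂ = 0.5 − d and p̄ is the pooled proportion. The precision half-width is 2.576 × 0.5/√n.

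**Step 1: reproduce Table 7 with no attrition.**

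| Row | Counts | Computed | Stated |
|---|---|---|---|
| Tier 2 infected v uninfected | 3,562 v 718 | 7.86% | 7.9% |
| Tier 2 PASC+ precision | 3,050 | ±2.33% | ±2.3% |
| Recovery, full sample | 2,440 v 610 | 8.69% | 8.7% |
| Recovery, 25% subgroup | 610 v 152.5 | 17.15% | 17.2% |
| Tier 2 PASC+ v PASC− | 3,050 v 512 | 9.16% | 10.0% |

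The first four rows match only with full counts. The last does not match. Its 10.0% corresponds to about 420 PASC− participants (9.98%), which the protocol does not explain; the row therefore already has some slack against 512.

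**Step 2: cap against N.** The cap is 0.30 × 14,880 = 4,464 assigned, equal to the stated N tested, so the required completion is 100%. The group counts sum to 3,050 + 512 + 718 = 4,280, and 4,280/14,880 = 28.8%. Testing 4,280 out of 4,464 assigned requires 4,280/4,464 = 95.9% completion overall.

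**Step 3: Tier 2 rows at assumed completion rates.** With the section 12.2 counts assigned and no reallocation:

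| Completion | Infected v uninfected | PASC+ precision |
|---|---|---|
| 95% | 8.06% | ±2.39% |
| 90% | 8.28% | ±2.46% |
| 80% | 8.78% | ±2.61% |

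Section 6.1 allows the sampling percentages to be modified. All 3,050 symptomatic infected participants are already included, so the spare 4,464 − 4,280 = 184 places can go only to controls. Assigning 3,050 + 892 uninfected + 522 infected without symptoms = 4,464, at 82% completion, leaves about 2,501, 731 and 428 tested. The comparison rows are then 7.94% and 10.03%, which round to the stated 7.9% and 10.0%. At 80%, with a near-identical split, they are 8.05% and 10.13%, narrowly missed.

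**Step 4: PASC+ precision.** A half-width that rounds to ±2.3% must be below 2.35%, so n ≥ (2.576 × 0.5/0.0235)² ≈ 3,004. That is 3,004/3,050 = 98.5% of the pool.

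**Step 5: recovery row at assumed loss.**

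| Loss | Evaluable | Full sample | 25% subgroup | Power at 8.7% |
|---|---|---|---|---|
| 10% | 2,745 | 9.16% | 18.05% | 86% |
| 20% | 2,440 | 9.71% | 19.09% | 81% |
| 30% | 2,135 | 10.37% | 20.35% | 74% |

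**The case against.** A reader might infer that the Tier 2 figures as a whole cannot be delivered. The document does not support that. The counts behind the table use 28.8% of participants rather than 30%, and the adaptive shares keep both comparison rows within the cap down to about 82% completion. This stands, and it confines the point to the stated N and the precision row.

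A reader might also infer that the cap shuts testing before the target is reached. The only explicit rule for ceasing assignment is the bucket rule, and the 30% is written as what the proportions are designed to achieve. What remains is that the text does not say which prevails.

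The losses should not be exaggerated. REDCap removes known safety exclusions before selection, many Tier 2 tests have no listed exclusion in Appendix 5, tests are requested where locally available, and nothing makes a single refusal final. But refusal is expressly allowed, and even slight non-completion breaks an N that needs 100%.

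The precision row is limited by the pool of 3,050, not by the cap, so changing the 30% rule would not repair it.

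On recovery, 25% PASC is described as conservative. At 30% the pool would be 0.30 × 12,200 = 3,660, which absorbs 1 − 3,050/3,660 = 16.7% loss at an unchanged 8.7%. Data collected before loss are also retained under section 7.4. Both are fair mitigations, but section 12.2 fixes 25% and states no retention rate.

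**Conclusion.** The point holds in limited form. Assigned and tested are treated as the same number, and the Tier 2 N of 4,464 cannot be met under a cap of 4,464 assignments unless everyone assigned completes the test. The group counts need 95.9% completion overall. The two Tier 2 comparison rows are not undeliverable: they survive to about 82% if spare places go to controls.

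The ±2.3% row needs about 98.5% of the PASC+ pool tested, and the 8.7% recovery row needs complete outcome ascertainment. The cost of missing them is moderate: ±2.5% to ±2.6% at 90% to 80% completion, and 9.2% to 10.4% at 10% to 30% loss.

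These sizes rest on assumed completion and loss rates, on PASC frequency at 25%, and on the inferred alpha and power.

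**What to change.** 1. In section 6.1, apply the 30% limit to completed, evaluable tests, in line with the bucket-closing rule in the preceding paragraph. Alternatively, keep it on assignments and restate the Tier 2 N and the Table 7 figures at a stated completion rate.
2. Reconcile 4,464 with the group sum of 4,280 in section 12.2.
3. Restate the PASC+ precision row at a stated completion rate and the recovery row at a stated retention rate.

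This takes one phrase in section 6.1 and a few figures in section 12.2. The downside is somewhat more test offers under the first option, or slightly less favourable stated figures under the second.
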